11.7 Schedule of Procedures and Observations

The schedule of procedures and observations for this study is summarized in Appendix D.

11.8 Blood Draws for Immune Marker Analysis

Research blood draws for immune marker analysis is optional for study participants.

Recent work from the [name] lab has demonstrated the critical role of the immune system in PDT efficacy. Because of the importance of the immune system for PDT efficacy, along with the potential for the immune system to mount an effective anti-tumor response, it would be beneficial to monitor immune markers (detailed in Section 2.6) for correlation between the I-PDT treatment and local or distant disease recurrence.

Blood samples will be collected via venipuncture for immune marker analysis. Samples will be collected using one 10 mL heparinized green-top collection tube. Tubes will be labeled with the participant's initials, participant's study number, clinical study number, protocol time point (i.e. prior to infusion of porfimer sodium, Day 0), dose, and protocol day.

Samples for immune marker analysis will be obtained on:

- Day of 1st I-PDT prior to laser light illumination
- 7-10 days following 1st I-PDT.

All subsequent follow-up evaluations (if feasible):

• Initial follow-up (approximately 4 weeks \pm 1 week following 1st I-PDT

NOTE: For subjects that need later 2^{nd} and 3^{rd} I-PDT sessions (as per Section 10.4), the research blood draws are taken per the physician's discretion.

Whole blood samples collected at RP will be sent at room temperature for processing the same day of collection.

The samples should be sent to:

Roswell Park Comprehensive Cancer Center Attn: Flow Cytometry – I 67918 [name] [name] (8:30 am -5 pm) [contact]

Note: All investigator or analyzing research laboratories housing research samples need to maintain current **Temperature Logs** and study-specific **Sample Tracking and Shipping Logs**. The Principal Investigator/Laboratory Manager **must** ensure that the stated lab(s) have a process in place to document the receipt/processing/storage/shipping of study-related samples/specimens.

11.9 Pathology

Standard pathologic analysis of resected head and neck tissue and tumor will be performed.

12.0 Withdrawal of Subjects

Subject Withdrawal

The subject will be withdrawn from the study as described in Section 10.5 and if:

- The I-PDT can't be administered.
- The patient would become hemodynamically unstable during I-PDT.

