4.0 Local and Study-Wide Number of Subjects

In the Phase 1 study, a maximum of 12 (four cohorts of 3) evaluable participants at Roswell Park, will be enrolled. The number of subjects required is a function of the unknown dose-toxicity.

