10.3 Definition of Dose-Limiting Toxicity

Dose Limiting Toxicities will include:

Any adverse events (AEs) that are \geq grade 4 that are possibly, probably, or definitely related to the I-PDT, by recording the occurrence of AE during the first 30 days post final I-PDT treatment using the revised the National Cancer Institute (NCI) Common Terminology Criteria for Adverse Events version 5.0 (CTCAE v5.0). Dose Limiting Toxicities will be evaluated for 30 days post final I-PDT day.

If participants experience DLTs, further I-PDT sessions will be held until DLT resolution as well as after porfimer sodium clearance.

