10.5 Treatment Discontinuation

All subjects who discontinue due to an AE must be followed until the event resolves or stabilizes. Appropriate medical care should be provided until signs and symptoms have abated, stabilized, or until abnormal laboratory findings have returned to acceptable or pre-study limits. The final status of the AE will be reported in the subject's medical records and the appropriate eCRF.

Reasons for treatment discontinuation should be classified as follows:

- Death
- Progressive disease
- Treatment-related toxicity
- Toxicity unrelated to treatment
- Investigator judgment
- The Investigator may withdraw a subject if, in his/her judgment, it is in the subject's best interest to do so.
- Noncompliance
- Subject voluntary withdrawal
 - A subject may withdraw from the study at any time, for any reason. If a subject discontinues treatment, an attempt should be made to obtain information regarding the reason for withdrawal.
- Early withdrawal of subject(s)
- Sponsor decision

Subjects who are unavailable for follow-up evaluations should be classified as lost to follow-up for 1 of the following reasons:

- Lost to follow-up: For a subject to be considered lost to follow-up, the investigator must make two attempts to re-establish contact with the subject. The attempts to re-establish subject contact must be documented (e.g., certified letter).
- Death: Date and cause of death will be recorded for those subjects who die within 30 days after treatment (telephone contact is acceptable).

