19.6 Adverse Events

The frequency of toxicities will be tabulated by grade across all dose levels and cycles. All subjects who receive any study treatment will be considered evaluable for toxicity.

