19.7 Interim Analysis and Criteria for Early Termination of the Study

A formal stopping rule for safety is given in Section 19.1. In addition, the Phase 1 study will be monitored and discussed by Roswell Park's Early Phase Clinical Trials Committee, which meets on a regular basis per the Roswell Park Data Safety Monitoring Plan. Drug safety will be monitored and evaluated continuously throughout the study including 30-day safety follow-up period by obtaining, reviewing and analyzing data on AEs, changes in laboratory values, vital signs, electrocardiograms (ECGs), and physical examination findings. Potential early termination decisions are an inherent part of the Phase 1 study monitoring.

Specific attention will be paid to incidents of:

- 1. Life threatening hemorrhaging
- 2. Airway compromise leading to emergency intubation or tracheostomy

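### Section 12.0 withdraws hemodynamically unstable patients from the study, not only from I-PDT, which can cut short the 30-day DLT observation that Section 10.3 requires

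*Combined protocol and SAP*

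**What the plan says.** Section 12.0 opens with "The subject will be withdrawn from the study as described in Section 10.5 and if" and lists two further conditions. The second is "The patient would become hemodynamically unstable during I-PDT". The withdrawal is from the study, yet the section it refers to, 10.5, is about treatment discontinuation.

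The other relevant text:

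- **Section 10.3** defines a DLT as an adverse event of grade 4 or higher "that are possibly, probably, or definitely related to the I-PDT", and sets the window: "Dose Limiting Toxicities will be evaluated for 30 days post final I-PDT day".
- **Section 10.4, Table 2** makes the dose decision. A level with at most 1 DLT in 6 is generally the recommended one, and at least 6 patients must be entered there.
- **Section 10.5** covers follow-up after stopping: "All subjects who discontinue due to an AE must be followed until the event resolves or stabilizes".
- **Section 19.6** states: "All subjects who receive any study treatment will be considered evaluable for toxicity".
- **Sections 17.3 and 17.4.1** collect adverse events and serious adverse events to 30 days after the last intervention. Neither makes an exception for withdrawal, but both allow collection to end sooner if a new treatment starts.
- **Section 4.0** plans for "a maximum of 12 (four cohorts of 3) evaluable participants" and does not define evaluability for the dose decision.
- **Section 19.7** calls for specific attention to "Life threatening hemorrhaging", a plausible cause of instability during the procedure.

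**The concern.** The trigger for leaving the study is itself a possible toxicity of the procedure. If withdrawal from the study is applied as written, the length of DLT observation depends on how the patient tolerated treatment, and observation is shortened in patients who have already had trouble.

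The recommended light irradiance dose is part of the primary objective, and it rests on very few patients. Table 2 separates 1 DLT in 6 from 2 in 6, so one unrecorded event can turn a rejected level into an accepted one. In the first cohort, one unrecorded event can turn 2 of 3, which sends the trial to Dose Level -1, into 1 of 3, which keeps it at Dose Level 1. A missed DLT can only push toward accepting a level.

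**Working it through.** **The plan's own figure.** The maximum of 12 reproduces: 2 dose levels × 6 patients = 4 cohorts × 3 = 12.

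**Which observation is at risk.**

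1. *Instability, or its cause, is grade 4 or higher and related.* It meets the 10.3 definition on the I-PDT day. Later withdrawal does not undo it, so nothing is lost for that patient's DLT status.
2. *Instability is below grade 4, and a separate related grade 4 or higher event follows within 30 days.* The later event is a DLT under 10.3. Section 10.5 obliges follow-up only of the event that led to stopping, which may resolve well before day 30. Sections 17.3 and 17.4.1 would collect the later event, unless a new treatment has started first. Section 9.0 says these patients would otherwise receive chemotherapy, targeted therapy or possibly immunotherapy, so an early new treatment is realistic. This is the gap.
3. *Instability with no DLT at any time.* Early loss of follow-up hides nothing, but the patient still belongs in the denominator.

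**Dose acceptance.** Let *p* be the true DLT rate and P(accept) the chance of at most 1 DLT in 6:

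P(accept) = (1−p)⁶ + 6p(1−p)⁵

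Working through the two cohorts of three in Table 2 gives the same value. At p = 0.33: 0.67⁶ + 6 × 0.33 × 0.67⁵ = 0.0905 + 0.2673 = 0.358.

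**Effect of missed DLTs.** Let *q* be the proportion unstable during I-PDT, and *m* the proportion of those with a DLT that goes unrecorded. The patients stay in the denominator, as 19.6 implies, so the observed rate is p − qm. The documents give no value for p, q or m; all are assumptions.

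| p | q | m | p − qm | P(accept), all DLTs seen | P(accept), some missed |
|---|---|---|---|---|---|
| 0.33 | 0.10 | 0.25 | 0.305 | 0.358 | 0.409 |
| 0.33 | 0.10 | 0.50 | 0.280 | 0.358 | 0.464 |
| 0.33 | 0.10 | 0.80 | 0.250 | 0.358 | 0.534 |
| 0.33 | 0.10 | 1.00 | 0.230 | 0.358 | 0.582 |
| 0.33 | 0.05 | 0.50 | 0.305 | 0.358 | 0.409 |
| 0.33 | 0.20 | 1.00 | 0.130 | 0.358 | 0.822 |
| 0.25 | 0.10 | 0.50 | 0.200 | 0.534 | 0.655 |
| 0.25 | 0.10 | 1.00 | 0.150 | 0.534 | 0.776 |
| 0.40 | 0.10 | 0.50 | 0.350 | 0.233 | 0.319 |
| 0.40 | 0.10 | 1.00 | 0.300 | 0.233 | 0.420 |

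Only case 2 contributes to m. Same-day DLTs (case 1) are already captured, so for a given q the values of m from 0.5 to 1.0 are an upper range, not a central estimate.

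**The case against.** The strongest reply is that the plan already keeps these patients under observation. A patient who becomes unstable during I-PDT has received porfimer sodium and is evaluable for toxicity under 19.6. Sections 17.3 and 17.4.1 run to 30 days without a withdrawal exception. Section 19.7 describes continuous safety monitoring that includes a 30-day follow-up. Section 12.0 refers to a section on stopping treatment, so its authors may have meant no more than that. The safety analysis in 19.3 and the notes to Appendix D even run the window from the first standard-of-care treatment, which points to longer collection.

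Most of this stands and limits the point. It does not close it. Section 19.6 is about tabulating toxicities and does not name the Table 2 denominator. The 19.3 and Appendix D windows do not match 10.3 or the new-treatment cut-off in 17.3 and 17.4.1. No section says that a patient withdrawn from the study under 12.0 completes the 30 days.

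A reader might go further and infer that Section 12.0 removes the patients most likely to have a DLT from the dose decision and lets them be replaced. The documents do not support that. No section takes them out of the DLT count, and none provides for replacement; the idea rests only on the undefined word for evaluability in 4.0. Nor does any figure show that unstable patients have the highest DLT risk. If they were dropped and replaced, the observed rate would be (p − qd)/(1 − q), with *d* the DLT rate among unstable patients. At p = 0.33 and q = 0.10, acceptance would be 0.396 for d = 0.5 and 0.521 for d = 1.0. For d = 0.25 it would fall slightly, to 0.340, so even the direction would depend on an unsupported assumption.

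**Conclusion.** The point holds in a limited form. Section 12.0, read literally, ends study participation because of a possible toxicity and is not reconciled with the 30-day DLT window in 10.3. What can be lost is a later related grade 4 or higher event in a patient whose instability was not itself a DLT. Treatment-day DLTs are not lost.

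The size cannot be derived from the documents. With an assumed 33% true DLT rate, 10% of patients unstable and a DLT missed in 50% to 100% of those, the chance of accepting the dose rises from about 0.36 to 0.46–0.58. Varying the proportion unstable from 5% to 20% widens this to 0.41–0.82. Because treatment-day DLTs are already counted, the real effect should lie toward or below the lower end for any given proportion unstable. The change is still worth making: it bears on the primary decision, and one event in six is enough to alter it.

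**What to change.** - **Section 12.0:** say that a patient who becomes hemodynamically unstable is discontinued from I-PDT but remains on study for the full 30-day safety follow-up, unless consent is withdrawn.
- **Section 10.3 and Table 2:** carry over the any-study-treatment rule of 19.6, so that these patients count in the DLT denominator and are not replaced because of an adverse event. Use the same definition for evaluability in 4.0.
- **Sections 10.5, 17.3 and 17.4.1:** cross-refer to the 10.3 window, and state that DLT assessment continues to day 30 even if a new treatment starts, with attribution recorded as usual.

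The criteria for stopping I-PDT are unchanged, and no view is taken on them. The cost is wording in an amendment; Appendix D already schedules a 30-day post-I-PDT visit with adverse event review.

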13.0 Risks to Subjects

This is a Greater Than Minimal Risk study according to IRB criteria. Phototoxicity is the most likely potential risk associated with the systemic administration of the porfimer sodium. Proper shielding from the procedure room lights will be maintained and the pulse oximetry sensor will be rotated every 15 minutes, to minimize this risk. The subjects will be provided with written instructions on how to protect themselves from excessive light exposure.

The site-specific toxicity associated with this therapy includes:

- a. **Injection site reaction:** Very common effects include pain at the injection site (12%) which is transient and can be minimized by slowing the injection rate. Common effects include injection site reaction (3%) and burning sensation (3%).
- b. **Tumor/local tissue reaction:** Very common effects include pain (15%), hemorrhage (15%) and scaring (12%). Common effects include edema (8%), localized infection (8%), fever (8%), and skin necrosis (2%).
- c. **Phototoxicity:** Common effects include sunburn (3%), blisters (5%), erythema (5%), hyper-pigmentation (3%), and cutaneous photosensitivity (3%).
- d. **Other systemic events:** Constipation (11%), vomiting (9%), anemia (8%), nausea (6%) and giddiness (2%).
- e. Collection of blood: Potential rare risks include local bleeding, inflammation and infection at the collection site (<1% of patients).

14.0 Potential Benefits to Subjects

For subjects that will have partial or complete response to I-PDT, the potential benefits include reduction in tumor related side effects (such as bleeding, pain, and dysphagia). Subjects that do not respond to I-PDT may not benefit from this treatment. In addition it has been shown, in other diseases sites, that PDT can improve OS and PFS when added to SoC therapy. Thus, it is possible that subjects that will respond to the experimental arm (I-PDT + SoC) will have increased OS and PFS. There is no guarantee of the outcome nor is it possible to predict whether or not the subject will respond to porfimer sodium-mediated I-PDT.

15.0 Data and Specimen Banking

Any clinical data that is associated with the samples will be stored on a secured server, will be accessible only by the PI, co-investigators and PI-designated data manager and, will be password protected. All computer entry and networking programs will be done using PIDs only.

Upon completion of sample assays the analyzing laboratories will provide results to Biostatistics and to CRS Data Management in a SAS compatible Excel file.

Note: All investigator or analyzing research laboratories housing research samples need to maintain current Temperature Logs and study-specific Sample Tracking and Shipping Logs. The Principal Investigator/Laboratory Manager must ensure that the stated lab(s) have a process in place to document the receipt/processing/storage/shipping of study-related samples/specimens. This is required for both observational and interventional clinical studies collecting clinical samples.

16.0 Measurement of Effect

16.1 Objective Disease Assessment

History, physical examination and standard CT will be used to monitor disease recurrence every 1-3 months in the first year, and every 2-6 in year 2, following the 2018 NCCN follow-up guidelines for patients with advanced HNC

(https://www.nccn.org/professionals/physician_gls/pdf/head-and-neck.pdf) (63; Appendix H). Subsequently, the treating physician will continue the usual clinical disease monitoring. Ancillary imaging studies such as PET-CT or MRI will be performed as indicated in the judgment of the treating physician based on findings from the history, physical examination or CT. Biopsy of suspected recurrent disease will be performed when feasible with minimal risk to the patient.

16.2 Target Lesions

The target lesions will be the locally advanced HNC that were treated with I-PDT or the ones that were identified by the principal investigator (or treating physician) as locally advanced and were treated with SoC therapy. Tumors measurements will take place 10-12 weeks after I-PDT or the first SoC in the control ram. Change in the target tumor size will be determine using the methods described in RECIST v1.1 (62). CT with contrast or MRI (when CT is not possible) will be used to determine change in tumor size. The objective response of the target tumor will be determined following these criteria:

- Complete Response (CR): Disappearance of all target lesions. Any lymph nodes must have a reduction in short axis to < 10 mm.
- Partial Response (PR): At least a 30% decrease in the sum of diameters of target lesions, taking as reference the baseline sum diameters. A biopsy will be taken from the suspected lesions for histological confirmation.
- **Progressive Disease (PD):** At least a 20% increase in the diameters of target lesions, taking as references the smallest sum on study (this includes the baseline sum if that is the smallest on study). In addition to the relative increase of 20%, the sum must also demonstrate an absolute increase of at least 5 mm.

• **Stable Disease (SD):** Neither, sufficient shrinkage to qualify for PR nor, sufficient increase to qualify for PD, taking as reference the smallest sum diameters while on study, the response will be listed with stable disease. In this case, a biopsy will be taken from the suspected lesion for histological confirmation.

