8.0 Study Endpoints

8.1 Primary Endpoints

Phase 1:

o The safety will be determined by recording the occurrence of AE during the first 30 days post final I-PDT day, using the revised NCI Common Terminology Criteria for Adverse Events (CTCAE) version 5.0.

Exploratory Endpoint

Objective target tumor response rates will be assessed according to RECIST v1.1 at 12 ± 2 weeks post I-PDT as described in section 16.2.

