9.0 Study Design

All participants will meet the inclusion and exclusion criteria summarized in Section 3.1 and Section 3.2 prior to taking part in this study.

This study will recruit subjects with HNC who failed to respond to standard therapy and are not candidates for salvage surgery or radiation therapy including re-irradiation. These HNC subjects would otherwise receive SoC chemotherapy, targeted therapy or potentially immunotherapy as first line palliative care treatment options.

All participants will receive I-PDT. All participants will have a standard diagnostic head and neck scan with CT or MRI, with or without contrast. Participants will be followed according to the 2018-NCCN follow-up guidelines (63; Appendix H) for patients with advanced HNC (https://www.nccn.org/professionals/physician_gls/pdf/head-and-neck.pdf). The study related visits would be up to 2 years, thus every 1-3 months in the first year, and every 2-6 months in the second year. The routine clinical follow up will be up to 5 years. The study schema is shown in

[figure not shown]
[figure not shown]

Figure 3 Study Schema

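### Section 16.2 keeps a control-arm limb in its target-lesion definition; read literally, it could let an unilluminated lesion into the exploratory response sum

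*Combined protocol and SAP*

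**What the plan says.** Section 8.1 takes the exploratory endpoint from section 16.2: "Objective target tumor response rates will be assessed according to RECIST v1.1 at 12 ± 2 weeks post I-PDT as described in section 16.2".

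The definition in that section gives two ways for a lesion to be a target, joined by an *or*: "The target lesions will be the locally advanced HNC that were treated with I-PDT or the ones that were identified by the principal investigator". The first is tumour that received I-PDT. The second is tumour that the investigator or the treating physician had classed "as locally advanced and were treated with SoC therapy". The next sentence repeats the alternation for timing: "Tumors measurements will take place 10-12 weeks after I-PDT or the first SoC in the control ram" (as printed; presumably *arm*).

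Partial response is judged on the total over all targets: "At least a 30% decrease in the sum of diameters of target lesions, taking as reference the baseline sum diameters". Progression needs at least a 20% increase from the smallest sum on study and at least 5 mm in absolute terms.

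The design has no control arm. Section 9.0 states: "All participants will receive I-PDT".

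SoC nevertheless remains in the plan for these participants. Section 19.3 counts safety from the first SoC day, or from the last I-PDT day if no SoC is given. Section 19.4 includes type of SoC in a Cox model. Appendix D places the clinic visit at the first day of SoC and times a CT from SoC. Appendix D 1 has a row for SoC.

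**The concern.** I-PDT is a local treatment, and the endpoint is response of the target tumour after it. The second limb of the definition asks only that a lesion was judged locally advanced and was treated with SoC. In a trial where everyone receives I-PDT and may then receive SoC, one participant could have an illuminated mass and another mass outside the light field, and on the literal wording both would qualify.

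Because response is read from a sum of diameters, an unlit lesion in that sum can dilute a real local response or supply a shrinkage that the illuminated tumour did not show. What is at stake is the classification of individual participants in the one exploratory objective, in a trial small enough for a single participant to be visible in the rate.

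**Working it through.** **Inputs from the documents**

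- Maximum sample size: 12, as four cohorts of three (section 4.0). Check: 4 × 3 = 12, which also equals two dose levels of at most six each under section 10.4. The figure reproduces and is not in dispute.
- At least six participants at the recommended dose (section 10.4, Table 2).
- Response rules on the sum of target diameters (section 16.2).
- Analysis: sample proportion with a 95% confidence interval (section 19.4). The interval method is not stated; exact (Clopper-Pearson) is assumed below.

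**Inputs assumed**

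The documents give no lesion sizes, so all diameters are illustrative. The baseline sum is taken as the smallest on study.

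**Step 1. How an added lesion acts on the sum**

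Change in sum = (sum at scan − baseline sum) / baseline sum. This is the average of the lesion changes weighted by baseline diameter. With two lesions of equal baseline size and the unlit one stable, the change in the sum is half the change in the lit lesion. The lit lesion would then have to shrink by 60%, not 30%, for the sum to reach −30%.

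**Step 2. Worked cases**

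| Case | Lit lesion, mm | Lit alone | Unlit lesion, mm | Sum, mm | Sum change |
|---|---|---|---|---|---|
| Response lost | 40 → 24 | −16/40 = −40%, PR | 40 → 40 | 80 → 64 | −16/80 = −20%, SD |
| Response gained | 40 → 38 | −2/40 = −5%, SD | 40 → 16 | 80 → 54 | −26/80 = −32.5%, PR |
| Response becomes progression | 40 → 28 | −12/40 = −30%, PR | 40 → 70 | 80 → 98 | +18/80 = +22.5% and +18 mm, PD |

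Misclassification can go in either direction.

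**Step 3. Effect on the rate**

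One reclassified participant moves the rate by 1/12 = 8.3 percentage points, or by 1/6 = 16.7 points if only six are treated. Exact 95% intervals at n=12:

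- 2/12 = 16.7% (2.1 to 48.4)
- 3/12 = 25.0% (5.5 to 57.2)
- 4/12 = 33.3% (9.9 to 65.1)

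A shift of one participant is small against the width of any of these intervals.

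**Step 4. Is the second limb closed off elsewhere?**

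No section limits target lesions to illuminated tumour. The eligibility criteria in section 3 do not limit the number of lesions. The references to SoC in sections 19.3 and 19.4 and in both schedules keep the literal reading open.

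**The case against.** The strongest reply is that the limb covers nobody. The sentence after it uses the same alternation and names a control arm. Section 14.0 still speaks of an experimental arm, and section 19.4 still has a yes/no factor for I-PDT. Read between arms, the first limb is for I-PDT patients and the second for controls, and there are no controls. This is the most likely origin of the text and probably what was meant. It stands as an explanation, but the wording does not say so, and SoC after I-PDT stops the limb from being empty on its face.

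The surrounding text also leans towards illuminated tumour. Section 8.1 speaks of target tumour response after I-PDT, eligibility requires a tumour accessible to illumination, and planning aims to cover the whole CTV. The problem needs a second measurable locally advanced lesion outside the light field, later treated with SoC and chosen as a target. The documents give no frequency for that. This stands too, so the worked cases show possibility and not expected size.

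A reader might infer from the past tense (lesions that *were treated*) that targets are picked after the outcome is known. The documents do not support that: section 10.2.2 has the CTV defined before treatment, and section 16.4 refers to lesions identified at baseline.

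A reader might also infer that limiting targets to lit lesions would give a pure measure of I-PDT. It would not. The SoC listed in Appendix D 1 is chemotherapy, targeted therapy or immunotherapy, and if it starts before the response scan it reaches lit lesions as well.

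**Conclusion.** The point holds as a defect in an endpoint rule. Section 16.2 carries a control-arm limb that does not fit a trial where everyone receives I-PDT and that, read literally, admits an unilluminated lesion to the target sum. If that occurs, a target-tumour response can be lost or gained, at 8.3 points per participant at n=12. This rests on the literal reading, on SoC following I-PDT in the same participant, and on assumed diameters.

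It would go too far to say that the reported rate will be distorted, or that the exploratory objective cannot measure I-PDT: the limb may never be applied, and its frequency of use is unknown. In the third worked case, treating the unlit lesion as non-target restores the target-tumour response, but if its growth is judged non-target progression, Table 1 of section 16.3 still makes the overall response progressive disease.

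Severity is minor. Only the exploratory endpoint is touched; the primary safety assessment, the DLT rules and the dose conclusion are not.

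**What to change.** 1. In section 16.2, delete the SoC alternative and the control-arm wording. State instead that target lesions are the measurable lesions inside the I-PDT CTV, listed at pre-treatment planning before light delivery, and that all other lesions are followed as non-target.
2. Report target-tumour response, which is the section 8.1 endpoint, separately from the overall response in Table 1 of section 16.3.
3. Record the SoC start date relative to the response scan and present it beside the rate, because the first change does not remove any effect of SoC on illuminated lesions.

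The cost is protocol wording and, if not already captured, one date per participant. The CTV is already drawn before treatment (section 10.2.2, step 3) and the non-target column already exists. No scans or participants are added, and the maximum of 12 is unchanged.
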